5 STUDY SETTING

Supported accommodation managed by HumanKind, Thames Reach, St Mungo's and Hillcrest Futures in locations in the UK.

Supported accommodation consists of a small flat with sleeping area, bathroom, a kitchen and living space. These are designed to allow an individual privacy and to minimise disturbance at nights. There is limited communal space in these facilities, this will maintain the privacy of participants as it will not be immediately obvious to other residents of their participation.

6 PARTICIPANT ELIGIBILITY CRITERIA

6.1 Inclusion criteria

- Over 18 years of age
- Living in supported accommodation
- Participant reported current opiate drug use
- Willing to wear biosensor device while living in supported accommodation
- Able to provide informed consent (not intoxicated at time of consent)
- Able to converse in and understand English

6.2 Exclusion criteria

- Does not meet one or more of the inclusion criteria
- Skin sensitivity to ECG electrode patch
- Broken skin over chest area
- Implanted pacemaker device in-situ
- Not suitable for enrolment in opinion of site staff or investigators

7 STUDY PROCEDURES

7.1 Recruitment

Potential participants are provided with study information during their registration at the participating supported accommodation or approached by the site staff if they are already residents. If they meet the inclusion and exclusion criteria, then informed consent is taken and the participant provided with the DC Mobile system.

Potential participants' residency within the supported accommodation is not conditional of taking part in the study.

7.1.1 Participant identification

Potential participants will be identified by site staff based on their existing knowledge of the population and by those who make themselves known by requesting injecting equipment (where sites provide this).

7.1.2 Screening

No formal screening processes.

7.1.3 Payment

Long term resident participants will receive £25 per week dependent on evidence of wearing the biosensor and the tablet remaining in situ in their residence.

Short term participants will receive £5 for returning the biosensor and tablet the morning after use. Up to a maximum of £25.

Participants will receive £20 for taking part in semi-structured interview and £10 for participation in a focus group.

To avoid supported accommodation keeping physical money on-site, where possible participant payments will be made using the Cash Out system (<https://tinyurl.com/mr9c75kn>). This involves the supported accommodation staff sending a text message to the participant, stating the cash value to be received. This text message can be presented at any PayPoint location and the participant will receive the cash value. If a participant does not have a mobile telephone, arrangements will be made to provide the participant with the cash sum or a shopping voucher of the corresponding value.

7.2 Consent

Due to the transient nature of the target population and the likelihood that some potential participants will only reside in the supported accommodation for one evening, it is important that study information can be provided and informed consent taken at the same time. This will limit missing out on potential participants. Although any potential participants who would like more time to consider participation will be granted it. Potential participants will be given a participant information sheet by site staff at an appropriate time. Either during registration, a welfare check or if a participant requests injecting equipment. Where potential participants may have literacy difficulties, a member of site staff will support in these instances. All accommodation staff who will take consent will be trained on the process by TCTU trial management staff.

Consent is ongoing, should a participant return after being away from their accommodation for a period of at least three days, provided they have followed study procedures, they will be asked if they would like to continue in the study and receive the biosensor and tablet as normal.

The PI retains overall responsibility for the conduct of research. This includes the taking of informed consent of participants at the sites. They will ensure that any person delegated responsibility to

participate in the informed consent process is duly authorised, trained and competent to participate according to the ethically approved protocol, principles of GCP and Declaration of Helsinki.

Consent will be taken by supported accommodation staff who will be trained in this process to GCP standards by a member of the trial management team who is authorised to do.

Where a participant requests to speak with a physician from the trial team the consent process will not be completed until the participant has spoken to the physician and had all their questions answered to their satisfaction.

For adults who lose capacity their previous wishes will remain legally binding and this will remain valid unless the protocol changes significantly. If the protocol changes significantly, a participant who has lost capacity will be withdrawn.

In all cases the PI or delegate will consult with carers and take note of any signs of objection or distress from the participant – the participant will be withdrawn if they raise objection.

Staff participants – site staff who take part in semi-structured interviews or focus groups will be provided with a participant information sheet in advance and consent taken by the researcher before the interview or focus group begins or a questionnaire is completed.

7.3 Baseline data

Baseline data will be collected at registration per schedule of procedures, Appendix 1 and as described below.

7.4 Study assessments

Participants will answer questions to determine their demographics such as age, BMI and gender at birth. If required, participant will be weighed and measured to calculate their BMI. Participants will be asked if they have any existing respiratory medical conditions. After wearing the biosensor, participants will complete a short satisfaction survey on their experience of PneumoWave DC. Participants should complete this at least once. Participants who stay at the site for a longer period may complete more than one to show fluctuating levels of acceptance. Participants will be asked to complete a drug use diary and an AIR tool to describe their drug use. Drug use and care is discussed with participants so these can be completed in the presence of and with support of, site staff.

During welfare checks, site staff will record any evidence of drug use in the pCRF. If a participant requires intervention due to a potential overdose event, site staff will record this in the pCRF, along with the level of intervention required, if the participant is unresponsive. Where possible the biosensor will be left on the participant during the intervention, and removed once the participant has sufficiently recovered or prior to leaving the facility (i.e. transfer to a medical facility).

A subsection of participants will be asked to partake in semi-structured interviews, lasting no longer than 60 minutes, to describe their experience wearing the device.

A further subsection of participants, including those who may have had an interview, will be asked to take part in focus groups to discuss the PneumoWave DC Mobile and the prototype for the Alert system and the perceived benefits or downsides it may have.

Staff from across all participating supported accommodation will be invited to take part in a semi-structured interview and/or a focus group to discuss their views on, perceived benefits of or barrier to use of the biosensor and DC Mobile system.

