9.5 Notification of deaths

Only in the unlikely event of death being related to the device will they be reported to Sponsor as SAEs as per Section 9.3.

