10.3.2 Primary outcome analysis

- Biosensor data analysed to determine whether or not an alarm would have been raised (and possibly the timing of the alarm)
- Staff measured outcomes reviewed to categorise whether there was cause for concern about the participant
- Above measures compared to determine either True Positive / False Positive / True Negative / True Positive events
- Sensitivity and Specificity are calculated for the complete data set (ideally with error bars calculated by an appropriate statistical method)

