10.4 Procedure(s) to account for missing or spurious data

Biosensor data will be reconciled with staff and patient reported data. Those that do not reconcile will be excluded.

10.5 Other statistical considerations.

N/A

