11 DATA MANAGEMENT

11.1 Data collection tools and source document identification

Data will be collected via:

Case report form to collect participant demographics, any existing respiratory conditions, record potential SIRD events and outcomes and record issue/return of biosensor and tablet.

AIR Tool Questionnaire to assess participants' drug use behaviours. Completed once during the study.

Drug use diary to establish drug use, immediately prior to and during site stay. Completed at participants' discretion.

Satisfaction survey, completed at least once during the study.

Cloud data management for app respiratory data. The variability of normal respiratory patterns will be analysed using proprietary algorithms, facilitated by PneumoWave. This is fully anonymous.

Semi-structured interviews and focus group. Detailed in section 7.5 (Qualitative assessments)

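### The overdose-recording trigger in section 7.4 is narrower than the CRF content in 11.1 and the reference in 10.3.2, so sensitivity may rest on intervention-level events alone

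*Protocol*

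**What the plan says.** Four parts of the protocol bear on what enters the staff record and how it is used.

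- **Section 7.4** gives staff two recording instructions. The first has no condition attached: "During welfare checks, site staff will record any evidence of drug use in the pCRF". The second concerns overdose and is conditional: "If a participant requires intervention due to a potential overdose event, site staff will record this in the pCRF". The sentence goes on "along with the level of intervention required, if the participant is unresponsive", and it is unclear whether that last condition limits the whole record or only the level of intervention.
- **Section 11.1** describes the CRF more broadly, as a form used to "record potential SIRD events and outcomes and record issue/return of biosensor and tablet". Intervention is not mentioned.
- **Section 10.3.2** builds the reference for the primary analysis from the staff record: "Staff measured outcomes reviewed to categorise whether there was cause for concern about the participant". This is compared with whether the algorithm would have raised an alarm, and "Sensitivity and Specificity are calculated for the complete data set".
- **Section 10.4** adds a rule for disagreement: "Biosensor data will be reconciled with staff and patient reported data. Those that do not reconcile will be excluded".

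**The concern.** Three descriptions of the reference event sit side by side: intervention required (7.4), potential SIRD event (11.1) and staff concern (10.3.2). Staff work from the procedures section, so the narrowest of the three may decide what is written down. A later review under 10.3.2 cannot categorise an event that never reached the form.

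The events most exposed are those that staff see or hear about but that pass without staff intervening. Evidence of drug use is recorded unconditionally, so such an event could appear on the form as drug use and nothing more. Section 2 wants the data to separate SIRD from breathing patterns after substance use that do not end in overdose. A self-resolving episode entered as drug use would fall into that comparison class. At stake are what the primary sensitivity means and how well the data used to refine the algorithm are labelled.

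**Working it through.** The protocol gives no event rate, sensitivity or specificity, and section 10.1 says that the target of about 50 rests on no calculation. There is no stated figure to reproduce, so the check traces the classification and then illustrates its effect.

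**Step 1: where an observed but unrecorded event goes.** Suppose a true event is seen or reported, needs no staff intervention, and is entered only as drug use.

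- No alarm: sensor and staff record agree that nothing happened. The period counts as a true negative, although the device missed an event.
- Alarm: under 10.3.2 alone it is a false positive. Under 10.4 it is more naturally a non-reconciling record and is excluded.

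In neither case does the event enter the denominator of sensitivity. (If 10.4 also removed staff-recorded events without an alarm, sensitivity would be 1 by construction. That is a separate conflict between 10.3.2 and 10.4 and is set aside here.)

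**Step 2: effect on sensitivity.** Let c be the share of true events that are recorded, Se_R the detection probability for recorded events and Se_U that for unrecorded ones.

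- Reported sensitivity = Se_R
- Sensitivity over all these events = c × Se_R + (1 − c) × Se_U
- Overstatement = (1 − c) × (Se_R − Se_U)

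The overstatement is zero when Se_U = Se_R, positive when unrecorded events are harder to detect, and negative when they are easier.

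**Step 3: illustrations. Every rate and event count is an assumption.**

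- 5 recorded events at 90% and 2 unrecorded at 60%: (5 × 0.9 + 2 × 0.6) / 7 = 5.7 / 7 = 0.81, against a reported 0.90.
- 5 recorded at 90% and 5 unrecorded at 60%: (4.5 + 3.0) / 10 = 0.75, against 0.90.
- 5 recorded and 5 unrecorded, all at 90%: (4.5 + 4.5) / 10 = 0.90, so no bias.

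A second set takes 50 participants for 28 nights each (50 × 28 = 1,400 participant-nights, which is generous because some residents stay one night). It assumes a 2% event rate (28 events), Se_R = 0.95, Se_U = 0.70 and true specificity 0.95.

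- 75% recorded: 0.75 × 0.95 + 0.25 × 0.70 = 0.887, against a reported 0.95.
- 50% recorded: 0.5 × 0.95 + 0.5 × 0.70 = 0.825, against 0.95.
- 25% recorded: 0.25 × 0.95 + 0.75 × 0.70 = 0.762, against 0.95.

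**Step 4: effect on specificity, if unmatched alarms are scored and not excluded.** With 50% recorded there are 1,372 true non-event nights and 14 unrecorded event nights.

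- True negatives: 1,372 × 0.95 + 14 × 0.30 = 1,303.4 + 4.2 = 1,307.6.
- Apparent specificity: 1,307.6 / 1,386 = 0.943, against 0.950.

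With 25% recorded it is 0.940. Specificity hardly moves; the exposure is in sensitivity.

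**The case against.** The strongest reply is that 7.4 says what happens when intervention is required and does not say that other events go unrecorded. Section 11.1 has no such condition, the table in 3.1 lists overdose among staff-measured outcomes, and the 10.3.2 reference is wider than intervention. The form itself is not shown, and a graded level of intervention may take in lesser staff responses. This stands: the protocol does not restrict recording to intervention events. It gives staff one explicit overdose trigger that is narrower than the purpose the record must serve.

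A reader might infer several stronger claims, which the documents do not support.

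- *Unrecorded overdoses are scored as non-events.* Nothing says so. Under 10.4 an alarm without a matching staff record would probably be excluded. Only the unrecorded event without an alarm clearly becomes a true negative.
- *Deaths or collapses found late are lost.* Such a finding would plausibly be recorded as a potential SIRD event with an outcome under 11.1, and would plainly concern staff.
- *No other route captures these events.* Section 9.2, and 9.5 with "Only in the unlikely event of death being related to the device will they be reported to Sponsor", limit safety reporting and not CRF recording. Section 10.4 also brings in patient-reported data, although the diary is described as covering drug use and is optional.
- *The share of alarms that are right would be badly understated.* That depends on scoring unmatched alarms as false positives, and 10.3.2 does not plan that measure.

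It is also fair that the illustrated gap in sensitivity comes entirely from the assumed detection rates, and that this is a feasibility study.

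**Conclusion.** The point holds as an inconsistency with a consequence for the primary analysis. Section 7.4 is narrower than 11.1 and 10.3.2. If staff follow it as written, sensitivity describes events that reached staff intervention, on either treatment of unmatched alarms.

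Sensitivity is overstated if milder, self-resolving events are harder to detect, which is plausible but not shown. The size cannot be fixed from the protocol: the assumed cases run from no bias to 0.75 against 0.90, or 0.762 against 0.95. The conclusion assumes that some events are seen or reported without staff intervention and that staff take the 7.4 wording literally. It is worth correcting because an event left off the form at the time is hard to recover later, while the correction is cheap.

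**What to change.** Reconcile 7.4 with 11.1. Have staff record every potential overdose or SIRD event that they see or are told of, whether or not staff intervened, and add one CRF field for how it was identified (seen, reported or found later). Make clear that the clause on unresponsiveness does not limit whether an event is recorded. Use the full set for the 10.3.2 classification, and show the result restricted to intervention events as a secondary line.

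The cost is one sentence, one CRF field and one extra line in the results. It changes recording and not care. Some added events will be less certain; the new field and the secondary line let a reader see how much depends on them. Checks are intermittent and the flats are private, so events that nobody sees or reports stay uncaptured. The report should state that as a limitation.

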7.5 Qualitative assessments

To understand the attitudes, feelings and perceptions of participants and staff about the acceptability of wearing the device through semi structured interviews, focus groups, satisfaction surveys and questionnaires.

7.6 Withdrawal criteria

Participants are free to withdraw at any time and are not obliged to give reason(s). The CI, PI or delegate will make a reasonable effort to ascertain the reason(s), both for those who express their right to withdraw and for those lost to follow up, while fully respecting the individual's rights. The investigator may withdraw a participant at any time if it is in the best interest of the participant and continuation in the study would be detrimental to the participant's wellbeing. A full explanation will be provided in these instances.

7.7 End of trial

The end of trial at all Sites is defined as last participant last visit. The Sponsor and /or CI have the right at any time to terminate the trial for clinical or administrative reasons.

The end of the trial will be reported to the Sponsor and Research Ethics Committee (REC) within 90 days, or 15 days if the trial is terminated prematurely. The CI will ensure that any appropriate follow up is arranged for all participants.

A final clinical trial report will be submitted to the CA within 1 year of the end of the trial and will also be provided to the Sponsor and REC.

8 STUDY DEVICE AND SOFTWARE

8.1 Name and description of investigational medicinal product(s)

The PneumoWave DC Mobile device comprises:

Hardware:

- Small, discreet, chest-worn Bluetooth biosensor (40mm diameter x 14 mm thick) mounting on an adhesive patch (single, off-the-shelf ECG electrode)

Software:

- Participant/Administrator mobile device app including user interface, storing and transmitting biosensor data
- Researcher dashboard to review anonymous historic biosensor data
- Backend cloud data management infrastructure for data storage.

Outwith of PneumoWave DC Mobile, proprietary Alert algorithms for retrospectively analysing data for signs of SIRD.

8.2 Regulatory status of the device

PneumoWave DC Mobile (PW-DCM) is a UKCA Class 1 medical device registered with MHRA, and a Declaration of Conformity with the UK Medical Devices Regulations 2002 is provided by PneumoWave.

8.3 Study restrictions

This study is purely observational.

8.4 Assessment of compliance with treatment

Compliance will be assessed by the downloading of anonymous respiratory patterns from devices that are returned by participants after use.

9 DEVICE SAFETY

9.1 Definitions

Term	Definition
Adverse Event (AE)	Any untoward medical occurrence, unintended disease or injury or any untoward clinical signs (including an abnormal laboratory finding) in subjects, PWUD or other persons whether or not related to the investigational medical device.
Adverse Device Effect (ADE)	Adverse event related to the use of an investigational medical device. NOTE 1- This includes any adverse event resulting from insufficiencies or inadequacies in the instructions for use, the deployment, the implantation, the installation, the operation, or any malfunction of the investigational medical device. NOTE 2- This includes any event that is a result of a use error or intentional abnormal use of the investigational medical device.
Serious Adverse Event (SAE)	A serious adverse event is any untoward medical occurrence that: 
• results in death• is life-threatening• requires inpatient hospitalisation or prolongation of existing hospitalisation• results in persistent or significant disability/incapacity• consists of a congenital anomaly or birth defect Other 'important medical events' may also be considered serious if they jeopardise the participant or require an intervention to prevent one of the above consequences. NOTE: The term "life-threatening" in the definition of "serious" refers to an event in which the participant was at risk of death at the time of the event; it does not refer to an event which hypothetically might have caused death if it were more severe.

Serious Adverse Device Effect (SADE)	Adverse device effect that has resulted in any of the consequences characteristic of a serious adverse event.
Unanticipated Serious Adverse Device Effect (USADE)	Serious adverse device effect which by its nature, incidence, severity or outcome has not been identified in the current version of the risk analysis report. 
 NOTE: Anticipated SADE (ASADE): an effect which by its nature, incidence, severity or outcome has been previously identified in the risk analysis report

9.2 Operational definitions for (S)AEs

Only (S)AEs deemed directly related to the wearing of the device while on study site premises will be reported by site staff to the research team.

As this population is expected to be actively using opioids and other illicit drugs, any events attributed to illicit drug use will not be reported as an (S)AE.

9.3 Recording and reporting of SAEs, SARs AND SUSARs

An AE related to the wearing of the device will be reported as a study outcome.

Only SAEs deemed to be directly related to participation in this study will be recorded and reported to Sponsor as necessary.

9.4 Responsibilities

Site staff:

- Confirmation of eligibility criteria

Research Team:

- Identifying AEs based on participant responses recorded in the CRF or interviews.

CI/medically qualified PI or delegate:

- Ensuring that AEs and ARs are recorded and reported to the sponsor in line with the requirements of the protocol.

9.5 Notification of deaths

Only in the unlikely event of death being related to the device will they be reported to Sponsor as SAEs as per Section 9.3.

9.6 Pregnancy reporting

Pregnancy is not a risk factor. A pregnant person may use this device.

If a pregnancy is reported by a participant, participant will be advised they can continue in the study if they wish or they can choose to withdraw. Pregnancies will not be followed up.

